Enhancing the Effects of Alcohol Treatment with Lamotrigine

Principal Investigator: [name], PhD, ABPP

ClinicalTrials.gov ID: NCT04770493

Date: February 02, 2021

Rationale

Alcohol use disorder (AUD) affects nearly one-third of adults in the United States during their lifetime. Excessive alcohol use causes myriad acute and long-term medical, psychological, and social problems. It carries an economic burden of \$249 billion annually. Although advances in pharmacotherapy have improved treatment options for adults with AUD, treatment options for youth are limited.

Adolescent and young adult alcohol use is a leading public health concern. The harmful effects of underage drinking are irrefutable and include premature death and possibly irreversible damage to the developing brain. In addition, adolescence is a critical period in the pathogenesis of AUD; an estimated 3 to 15% of youth develop AUD before age 18. Clinical trials have tested psychosocial interventions with youth, including family treatments, cognitive behavior therapy (CBT), and motivational enhancement therapy (MET), that yield only modest short-term benefits. Our group has contributed substantially to this work.

One potential way to improve treatments is to augment psychosocial interventions with pharmacotherapy. The National Institute on Alcohol Abuse and Alcoholism (NIAAA) has mounted a concerted effort to identify medications that reduce drinking for nearly three decades. Although this effort improved treatment for adults, no medication is indicated for adolescent use, and randomized controlled trials with teenagers are almost nonexistent. This gap raises key questions about if and how medications could benefit youth. The urgency of this issue is underscored by the fact that optimizing treatment options for youth requires closing this critical gap.

Anticonvulsants are increasingly found to be efficacious for treating AUD. Many have intolerable side effects, however, that greatly limit their utility. Lamotrigine is a new generation mood-stabilizing anticonvulsant approved by the FDA to treat epilepsy in patients two and older and bipolar disorder in adults with fewer side effects than older anticonvulsants. We propose to study lamotrigine for three primary reasons.

- First, lamotrigine is safe and well tolerated by youth.
- Second, lamotrigine targets brain mechanisms implicated in the pathogenesis of AUD, namely the glutamatergic system, which mediates the acute and chronic effects of alcohol.
- Third, mounting human research that shows lamotrigine reduces alcohol and other substance use as well as craving.

On the whole, modulation of the glutamatergic system is a key pharmacological target for AUD treatment. Anticonvulsants reduce alcohol and other drug use in adults and adolescents but are not well tolerated. There is strong preclinical and emerging clinical

evidence that lamotrigine also reduces alcohol and other drug use, and human studies show it is well tolerated.

Objectives

The primary objectives of this study are twofold. The first primary objective is to evaluate the feasibility, acceptability, and tolerability of lamotrigine (25 mg/day to 200 mg/day in two divided doses) as compared to placebo for 9 weeks plus a psychosocial platform comprised of motivational enhancement therapy and cognitive behavioral therapy (MET-CBT; “Path 180”) among adolescents and young adults (ages 16 to 24 years) with AUD as confirmed by the Diagnostic and Statistical Manual of Mental Disorders – Fifth Edition (DSM-5™).

The second primary objective is to leverage a human laboratory paradigm to evaluate the effects of lamotrigine on an intermediate phenotype associated with alcohol use and outcomes in clinical trials. Specifically, we hypothesize that lamotrigine, as compared to placebo, will decrease alcohol cue-elicited craving in the human laboratory during in vivo alcohol cue reactivity.

Methodology

This proof-of-concept study is a double-blind, randomized, placebo-controlled, parallel group, single-site clinical trial. After obtaining consent/parent permission/assent, potential subjects and, if younger than 18 years, their parent(s) will complete a medical history and psychiatric diagnosis interview (about the adolescent) to screen for eligibility. Youth will also complete a physical examination, vital signs, drinking history and an alcohol breathalyzer test.

Forty-four eligible subjects will be randomized in an approximate 1:1 ratio to either lamotrigine or placebo for 9 weeks.

Dose titration, maintenance and taper will occur as scheduled below. Lamotrigine will be self-administered by subjects once daily after eating and with a full glass of water beginning on Study Week 1, Day 1 and continuing through Study Week 11, Day 7. The first dose will be taken in the study clinic whenever possible. Subjects will be provided with water and a snack to take with first dose. Dose will be titrated, as tolerated, to a target dose of 200 mg in two divided doses per day of lamotrigine. Following the target dose period, participants will complete a 2-week medication taper period (see dosing schedule below). Capsules should be swallowed whole and should not be cut, crushed, or chewed. Capsules should be taken with food and water.

Schedule of Administration of Investigational Product

Study Period	Time Period	Daily Dose	Dosing Schedule
Titration	Weeks 1-2	25 mg	Once daily
	Weeks 3-4	50 mg	Two divided doses
	Week 5	100 mg	Two divided doses
	Week 6	150 mg	Two divided doses
Maintenance	Week 7-9	200 mg	Two divided doses
Taper	Week 10	100 mg	Two divided doses
	Week 11	50 mg	Two divided doses

At the randomization/baseline visit and after 7 weeks of investigational product administration (i.e., Study Week 8), subjects will undergo a human laboratory paradigm (i.e., alcohol cue reactivity assessment).

Main Inclusion/Exclusion Criteria: Subjects will be male and female adolescents, ages 16 to 24 years old, who meet DSM-5 criteria for AUD. They must be seeking to reduce their alcohol use.

Investigational Product, Dosage and Mode of Administration: Lamotrigine (titrated for 6 weeks; target dose [200 mg/day/BID] for 3 weeks) will be over encapsulated and supplied by a contracted pharmacy, along with identical matching placebo capsules.

Reference Therapy, Dosage and Mode of Administration: Identically over encapsulated placebo tablets will be dispensed according to the same schedule as the lamotrigine capsules.

Statistical Analysis Plan

Primary Objectives

- Feasibility of retention will be determined by the percentage of enrolled subjects who complete the protocol (target $\geq 70\%$) and treatment-specific retention rates.
- Acceptability will be determined based on overall study withdrawal rates ($\leq 20\%$ considered acceptable), as well as treatment-specific withdrawal rates. Treatment satisfaction will be considered acceptable if $\geq 80\%$ of responses on the CSQ-8 are rated

either “satisfactory” or “highly satisfactory.” We will also examine reasons for termination qualitatively.

Secondary Objectives

- We hypothesize that lamotrigine, as compared to placebo, will decrease alcohol craving during an alcohol cue-exposure paradigm in the human laboratory.

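### The administration sentence sets once-daily dosing through the end of Week 11, while the schedule table splits the daily dose from Week 3 to Week 11

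*Combined protocol and SAP*

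**What the plan says.** The dosing paragraph under Methodology opens by referring to the schedule: "Dose titration, maintenance and taper will occur as scheduled below". Its next sentence sets the frequency: "Lamotrigine will be self-administered by subjects once daily after eating and with a full glass of water". That sentence also fixes the period to which the frequency applies, namely "beginning on Study Week 1, Day 1 and continuing through Study Week 11, Day 7". It makes no exception for any week.

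The same paragraph then gives the target: "Dose will be titrated, as tolerated, to a target dose of 200 mg in two divided doses per day of lamotrigine". The table that follows (Schedule of Administration of Investigational Product) has seven rows. The Weeks 1-2 row is once daily. The six rows covering Weeks 3-11 all specify divided dosing.

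Two other places bear on the point. The product description gives "Lamotrigine (titrated for 6 weeks; target dose [200 mg/day/BID] for 3 weeks", and the reference-therapy paragraph says that placebo is "dispensed according to the same schedule as the lamotrigine capsules". The Objectives give a range of 25 to 200 mg/day followed by a divided-dose phrase. It is unclear whether that phrase applies to 200 mg/day alone or to the whole range.

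**The concern.** The sentence and the table give different frequencies for the same weeks, and neither is stated to take precedence. A subject or pharmacist following the sentence would have the whole daily amount taken at once. One following the table would have it split.

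Subjects dose themselves. The only administration that the documents place in the clinic is the first ("The first dose will be taken in the study clinic whenever possible"), in Week 1, when the two texts agree. The first primary objective includes tolerability, so the regimen being evaluated should have one defined frequency in each period. The on-treatment cue-reactivity session in Study Week 8 also falls in the conflicting weeks. Because placebo follows the lamotrigine schedule, the ambiguity reaches both arms.

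**Working it through.** The plan states no count of administrations, so there is no figure to reproduce. The check sets the two texts side by side and counts days and intakes.

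**Inputs.** Frequency and dates under the sentence: the dosing paragraph. Daily dose, weeks and frequency by row: the schedule table. Period lengths: the product description (6 weeks of titration, 3 at target) and the dosing paragraph (2-week taper).

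**Duration.** The table gives 2 + 2 + 1 + 1 = 6 weeks of titration, 3 of maintenance and 1 + 1 = 2 of taper. That is 11 weeks, or 77 days. It matches the stated lengths and the sentence's end date, so the two texts cover the same period.

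**Row by row.** Intakes = days × intakes per day; mg in period = days × daily dose.

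| Weeks | Days | Daily dose (mg) | Intakes/day, sentence | Intakes/day, table | Intakes, sentence | Intakes, table | mg in period |
|---|---|---|---|---|---|---|---|
| 1-2 | 14 | 25 | 1 | 1 | 14 | 14 | 350 |
| 3-4 | 14 | 50 | 1 | 2 | 14 | 28 | 700 |
| 5 | 7 | 100 | 1 | 2 | 7 | 14 | 700 |
| 6 | 7 | 150 | 1 | 2 | 7 | 14 | 1,050 |
| 7-9 | 21 | 200 | 1 | 2 | 21 | 42 | 4,200 |
| 10 | 7 | 100 | 1 | 2 | 7 | 14 | 700 |
| 11 | 7 | 50 | 1 | 2 | 7 | 14 | 350 |
| Total | 77 | | | | 77 | 140 | 8,050 |

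**Extent of conflict.** Six of 7 rows and 9 of 11 weeks. In days, 77 − 14 = 63, and 63/77 = 81.8%.

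**Total dose.** With full titration, the cumulative scheduled dose is 8,050 mg under either reading. The amount per day does not differ.

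**Amount at one time.** If the divided doses are equal halves, which the documents do not state, the single intake (sentence v table) is:
- Weeks 3-4 and Week 11: 50 v 25 mg
- Weeks 5 and 10: 100 v 50 mg
- Week 6: 150 v 75 mg
- Weeks 7-9: 200 v 100 mg

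**Without the table.** At 200 mg/day the dosing paragraph contradicts itself, because its target sentence specifies divided dosing. The product description (BID) agrees with that target sentence. The 21-day length of this period comes from the table and the product description, not from the paragraph. For the other conflicting weeks the conflict rests mainly on the table. The Objectives phrase would add to it only if it covers the whole range, and on that reading it would also disagree with the table's once-daily 25 mg step.

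**The case against.** The paragraph begins by deferring to the schedule and points to it again for the taper. The schedule is complete row by row, and the target sentence and product description both specify divided dosing. One sentence is the outlier, so staff may well notice the conflict. The labels and pharmacy documents, which are not available here, may already be consistent. Daily dose and period lengths agree throughout, and the listed analyses (retention, withdrawal, satisfaction ratings, reasons for termination) do not depend on frequency. On this view it is a wording slip with no demonstrated consequence.

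Much of this stands. No harm to subjects and no effect on a trial conclusion is shown. The cumulative dose measures no discrepancy, and the per-intake amounts rest on an assumption. The tolerability link is a reason to define the regimen, not evidence of bias. What does not stand is that the reference to the schedule settles the matter: it states no precedence, and a once-daily instruction dated to the last day of the taper cannot be read as meaning Weeks 1-2 only. How staff would probably interpret the text does not replace a stated instruction.

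**Conclusion.** The contradiction is real and must be corrected. Frequency conflicts in every week from 3 to 11: 82% of treatment days, with 77 against 140 administrations per subject. These counts assume completion of the full 11-week schedule and a literal reading of each text. The per-intake comparison further assumes full titration and equal halves. The finding is limited to frequency, and so to the amount taken at one time. Its weight comes from the kind of text involved: a self-administration instruction that cannot be followed as written on most treatment days.

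**What to change.** Reconcile the administration sentence with the schedule table so that each study period carries a single stated frequency, and make the target sentence and product description agree with the result. Clarify in the Objectives which doses the divided-dose phrase covers. Then check that labels and subject instructions for both arms match the reconciled text. The choice of frequency belongs to the sponsor, and none is proposed here.

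The cost is a wording correction to one sentence and one parenthetical, plus the check of labels and instructions. Sample size, visits and analyses are unaffected.

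### The acceptability bar counts only study withdrawal, so it can be met whatever share of the lamotrigine arm has stopped capsules

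*Combined protocol and SAP*

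**What the plan says.** Under Objectives, the earlier of the two main aims reads: "evaluate the feasibility, acceptability, and tolerability of lamotrigine (25 mg/day to 200 mg/day in two divided doses) as compared to placebo for 9 weeks". Both arms also receive a MET-CBT platform. Under Methodology, "Forty-four eligible subjects will be randomized in an approximate 1:1 ratio to either lamotrigine or placebo for 9 weeks". Subjects take the capsules themselves, and "Dose will be titrated, as tolerated, to a target dose of 200 mg in two divided doses per day of lamotrigine". The administration schedule puts the target in Weeks 7 to 9 and a taper in Weeks 10 and 11.

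The Statistical Analysis Plan, under Primary Objectives, sets three numeric bars:

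- **Feasibility:** "Feasibility of retention will be determined by the percentage of enrolled subjects who complete the protocol", with a target of at least 70%, "and treatment-specific retention rates". What counts as completing the protocol is not defined.
- **Acceptability, withdrawal:** "Acceptability will be determined based on overall study withdrawal rates", with at most 20% regarded as acceptable, "as well as treatment-specific withdrawal rates". The arm-level rates carry no threshold.
- **Acceptability, satisfaction:** "Treatment satisfaction will be considered acceptable if" at least 80% of CSQ-8 responses fall in the two favourable categories.

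Reasons for termination are reviewed qualitatively. Tolerability, which the objective names, has no criterion in the SAP. Neither does capsule discontinuation, adherence or dose reached.

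**The concern.** The objective is about a drug, while the withdrawal bar is about leaving a study. The two can diverge here because every subject also receives psychosocial treatment and must be seeking to reduce drinking. That gives a subject a reason to keep attending after stopping capsules. Nothing in the documents says that stopping capsules ends participation, so such a subject is not a study withdrawal. The arm-specific withdrawal rates have the same gap, because they also count departures from the study.

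At stake is what a met bar means. A low withdrawal rate could reflect willingness to stay in a study that provides MET-CBT, and be read as evidence that young people accept and tolerate lamotrigine. The Rationale describes anticonvulsants generally as poorly tolerated and presents lamotrigine as the exception, so whether subjects stay on this drug is close to the centre of the question.

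**Working it through.** **Inputs from the documents:** 44 randomized, about 1:1; bars of at least 70% completing and at most 20% withdrawing. The sample size comes without alpha, power, effect size or precision, so it cannot be reproduced. It is not in dispute here.

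**Assumptions:** 22 per arm; the 44 randomized as the denominator of both bars; study withdrawal *w* = 10% or 15% in each arm; a further share *q* of the whole lamotrigine arm (0 to 40%) stops capsules but stays; no such stops on placebo. The documents give none of these rates.

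**Step 1: bars as counts.**
- Withdrawal: 0.20 × 44 = 8.8, so at most 8 (8/44 = 18.2%; 9/44 = 20.5% would fail).
- Completion: 0.70 × 44 = 30.8, so at least 31 (31/44 = 70.5%).

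**Step 2: a direct count.** Suppose 2 subjects per arm leave the study and 8 more lamotrigine subjects stop capsules but keep attending.
- Study withdrawal: 4/44 = 9.1%, bar met.
- Retention: 40/44 = 90.9%, bar met if completion means staying.
- Lamotrigine subjects still on capsules: (22 − 2 − 8)/22 = 12/22 = 54.5%.
- Withdrawal if capsule stops counted: (4 + 8)/44 = 27.3%, above 20%; in the lamotrigine arm, 10/22 = 45.5%.

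In the limit, all 22 lamotrigine subjects stop capsules and everyone stays: study withdrawal is 0/44 = 0% and the bar is met.

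**Step 3: chance of meeting the withdrawal bar.** As written, this is P(X + Y ≤ 8), with X and Y independent Binomial(22, *w*). If capsule stops count, X becomes Binomial(22, *w* + *q*). Exact results:

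| *q* | *w* = 10%, as written | *w* = 10%, stops counted | *w* = 15%, as written | *w* = 15%, stops counted |
|---|---|---|---|---|
| 0 | 0.972 | 0.972 | 0.794 | 0.794 |
| 10% | 0.972 | 0.796 | 0.794 | 0.469 |
| 20% | 0.972 | 0.467 | 0.794 | 0.187 |
| 30% | 0.972 | 0.177 | 0.794 | 0.047 |
| 40% | 0.972 | 0.040 | 0.794 | 0.007 |

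The as-written columns do not move with *q*.

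**Step 4: the feasibility bar, which depends on the definition.** At least 31 completers means at most 44 − 31 = 13 losses. With *q* = 30%, the chance of meeting the bar is about 1.000 (*w* = 10%) or 0.996 (*w* = 15%) if completion means staying. It is 0.824 or 0.549 if completion requires being on capsules. The missing definition therefore matters, but the effect is smaller than for the withdrawal bar.

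**The case against.** Retention and withdrawal are ordinary measures for a proof-of-concept study and need not also measure exposure. Stopping a drug for side effects is a tolerability matter. That is fair, but tolerability is part of the same objective and has no criterion, so the gap is not filled elsewhere.

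Three stronger readings are tempting, and the documents do not support them.

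- **A poorly tolerated regimen would be declared feasible and acceptable overall.** This does not follow. There is a third bar, on CSQ-8 satisfaction, and reasons for termination are reviewed. Completing the protocol might also require taking capsules, since dosing runs through Week 11. The label given to the feasibility criterion, and its pairing with retention rates, favour the stay-or-leave reading but do not settle it. What stands is that neither the CSQ-8 bar nor the review of reasons is stated to measure drug exposure.
- **A subject who never reaches 200 mg is a failure scored as a success.** The objective names a range of 25 to 200 mg/day, and titration is as tolerated. A subject below target may be following the regimen as described.
- **The 70% target should apply to on-capsule status in the lamotrigine arm.** That target was set for all enrolled subjects. The documents give no basis for using it as a gate on one arm of about 22.

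It is also true that every discontinuation rate used above is assumed. The insensitivity of the withdrawal bar to those rates is not an assumption. It follows from what the bar counts.

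**Conclusion.** The point holds for the acceptability bar. As worded, it responds only to study withdrawal, so at 44 subjects it is met with 8 or fewer departures regardless of how many lamotrigine subjects have stopped capsules. With 10% withdrawal per arm and a further 30% of the lamotrigine arm off capsules, the probability of meeting it is 0.972 as written, against 0.177 if stops counted; with 15% withdrawal, 0.794 against 0.047. These figures rest on 22 per arm, independent subjects and the assumed rates. They also assume that subjects who stop capsules may stay, which the documents neither state nor rule out.

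For feasibility the point is conditional on what completion means. The randomized design is unaffected. What suffers is the link between a met bar and a statement about the drug.

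**What to change.** Keep the three stated bars and make these changes to the SAP, under Primary Objectives:

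1. State whether completing the protocol requires taking capsules.
2. Count permanent capsule discontinuation as treatment withdrawal, separately from study withdrawal and whether or not the subject stays in MET-CBT. Present it by arm within the primary acceptability and tolerability determination.
3. Beside it, give by arm the percentage of randomized subjects on capsules at the end of Week 9 and the percentage who reached the scheduled target. The latter is descriptive; falling short of target is not to be scored as failure.
4. State that lamotrigine will not be concluded acceptable or tolerable from study withdrawal alone.

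No dosing rule changes, and no 70% gate is placed on the lamotrigine arm alone. The cost is SAP wording and a little more analysis from dispensing and dose records. Those records are assumed to be kept, since the documents do not describe them. The conclusion may also turn out less favourable.

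### Does the CSQ-8 satisfaction benchmark need a by-arm figure, a defined unit and a stated visit before it can be used?

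*Combined protocol and SAP*

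**What the plan says.** The first primary objective concerns feasibility, acceptability and tolerability of lamotrigine "as compared to placebo for 9 weeks plus a psychosocial platform comprised of motivational enhancement therapy and cognitive behavioral therapy" (Objectives). As this reads, both arms receive the psychosocial platform.

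The Statistical Analysis Plan, under Primary Objectives, sets three benchmarks:

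- **Retention.** "Feasibility of retention will be determined by the percentage of enrolled subjects who complete the protocol", with a target of at least 70%, "and treatment-specific retention rates".
- **Withdrawal.** "Acceptability will be determined based on overall study withdrawal rates", with 20% or less counted as acceptable, "as well as treatment-specific withdrawal rates".
- **Satisfaction.** Acceptable if at least 80% "of responses on the CSQ-8 are rated" in one of two favourable categories.

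The acceptability bullet then closes with "We will also examine reasons for termination qualitatively". The CSQ-8 is mentioned nowhere else. None of the three benchmarks has a pass threshold per arm.

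**The concern.** The authors put a by-arm rate beside the overall figure twice and left it out the third time. Satisfaction seems to need it at least as much. If everyone receives MET-CBT, ratings of that shared platform enter both arms, and a single pooled percentage could pass mainly because participants liked the therapy. Only the contrast between arms bears on lamotrigine against placebo.

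Two further details look open. The sentence does not define a response, which could be one item rating or one participant. It also gives no week for the questionnaire. At stake would be a primary-objective benchmark that passes while satisfaction on lamotrigine is below 80%, or whose unit is chosen after the data are seen.

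**Working it through.** The 80% is a chosen threshold. The plan gives no derivation, power or sample-size calculation, so there is no stated figure to reproduce. What can be checked is how much a pooled pass could hide, and how much a by-arm figure would reveal.

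**Inputs from the plan.** 44 randomised, approximately 1:1 (22 per arm if equal); withdrawal acceptable up to 20%; satisfaction benchmark 80%.

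**Assumptions, not in the plan.** A response is one item rating; 8 items per form (inferred from the instrument's name); one form per person; withdrawers return none; withdrawals split evenly; within-person correlation (ICC) 0.2 to 0.6.

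**Step 1: lowest pooled pass.**
- Withdrawals at the limit: floor(0.20 × 44) = 8, leaving 36 responders, 18 per arm.
- Ratings: 18 × 8 = 144 per arm, 288 in all. Lowest pass: ceil(0.8 × 288) = 231, or 80.2%.
- That total fits 109/144 (75.7%) on lamotrigine with 122/144 (84.7%) on placebo, or 101/144 (70.1%) with 130/144 (90.3%).
- With all 44 responding: 352 ratings, lowest pass 282 (80.1%), which fits 132/176 (75.0%) with 150/176 (85.2%).

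So a pooled pass can coexist with a lamotrigine figure below 80%. These splits were picked at the pass boundary; they show what is possible, not what is likely.

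**Step 2: how often.** Beta-binomial simulation, 18 per arm, 8 items, 100,000 trials per setting, ICC 0.2, 0.4 and 0.6:

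| True rates (lamotrigine / placebo) | Pooled benchmark passes | Passes with lamotrigine below 80% |
|---|---|---|
| 75% / 90% | 70–77% | 43–59% |
| 75% / 85% | about 51% | 26–34% |
| 80% / 80% | 51–52% | about 13% |
| 85% / 85% | 85–93% | 11–13% |

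The last two rows matter. With no difference between arms, the same pattern appears in about 11 to 13% of trials by chance, so the upper rows cannot be read wholly as concealed harm.

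**Step 3: what a by-arm figure could show.** The 95% half-width per arm is 1.96 × sqrt(p(1−p)(1 + 7 × ICC)/144). At p = 0.80, p(1−p) = 0.16:
- ICC 0.2: 1.96 × sqrt(0.16 × 2.4/144) = 10.1 points
- ICC 0.4: 1.96 × sqrt(0.16 × 3.8/144) = 12.7 points
- ICC 0.6: 1.96 × sqrt(0.16 × 5.2/144) = 14.9 points

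Multiplying by sqrt(2) gives 14.3, 18.0 and 21.1 points for the difference. At 75% against 90%, replace 2 × 0.16 by 0.1875 + 0.09 = 0.2775: the half-widths are 13.3, 16.8 and 19.6 points against a true gap of 15. A 10-point gap is inside the noise throughout, and a 15-point gap is borderline at best.

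**Step 4: effect on the verdict.** Adding by-arm percentages leaves the pooled count and the 80% threshold untouched, so pass or fail is identical in every setting above.

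**Step 5: the text on unit and arm.** The noun is responses and the verb is rated, which points to item ratings. The withdrawal criterion is expressly an overall rate; the satisfaction sentence has no such word. It follows directly on the treatment-specific clause in the same bullet ("as well as treatment-specific withdrawal rates. Treatment satisfaction will be considered acceptable if"). Pooling is therefore one reading, and showing the result by arm is an equally fair one.

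**The case for a change.** The best argument for a change is that the unit can alter the verdict. If each item is independently favourable with probability 0.80, the expected share of favourable items is 80%. Yet only 50.3% of participants would have at least 7 of 8 favourable items, and about 80% would have at least 6 of 8. Someone who scored participants could reach a different answer depending on the cut-off, and settling this beforehand costs a sentence or two.

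The arithmetic stands. But scoring participants requires a cut-off that the plan does not contain, so an analyst would have to invent one to leave the item reading. Following the sentence as written leads to item ratings. Writing a participant cut-off into the plan would add a rule with no basis in the documents.

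The missing by-arm clause and the missing visit also stand as matters of fact. The document is a short summary; the only outcome assessment to which it gives a week is cue reactivity (baseline and Study Week 8). The absent CSQ-8 visit reflects that level of detail and is not peculiar to this benchmark.

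**Conclusion.** No change to the plan is called for. This is a gap in reporting detail that analysts fill sensibly: the benchmark is descriptive, computable on its natural reading, and gives the same pass or fail whether or not by-arm percentages stand beside it. The concern is right that a pooled pass can coexist with a lower lamotrigine figure. How often depends on satisfaction rates and correlations that the plan does not give, and about 11 to 13% arises with no difference at all. The by-arm contrast would be too imprecise to settle the comparative question, with a half-width of about 14 to 21 points for 18 responders per arm.

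This rests on reading a response as an item rating, on 8 items per form and on the assumed correlations. The report should still show the CSQ-8 percentage by arm and say when it was collected, as description without an arm-level pass rule.
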